## **2. LIST OF ABBREVIATIONS**

Term	Definition / description
ACE	Angiotensin Converting Enzyme
AE	Adverse event
AESI	Adverse event of special interest
ALT	Alanine transaminase
ANCOVA	Analysis of covariance
ARB	Angiotensin Receptor Blocker
ARNI	Angiotensin Receptor blocker-Nepriylsin Inhibitor
ASA	Acetylsalicylic acid
AST	Aspartate transaminase
ATC	Anatomical-Therapeutic-Chemical
BI	Boehringer Ingelheim
BicMQ	Boehringer Ingelheim customized MedDRA Query
BMI	Body mass index
BP	Blood pressure
CCB	Calcium channel blocker
CEC	Clinical Event Committee
CI	Confidence interval
CIF	Cumulative Incidence Function
CKD-EPI	Chronic Kidney Disease Epidemiology Collaboration
CRF	Case report form
CRT	Cardiac resynchronisation therapy
CTP	Clinical Trial Protocol
CTR	Clinical Trial Report
CV	Cardiovascular
DBL	Data base lock
DBP	Diastolic Blood Pressure
DKA	Diabetic ketoacidosis
DM	Diabetes mellitus
DM&SM	Data Management and Statistics Manual
ECG	Electrocardiogram
eCRF	Electronic Case Report Form

---

Term	Definition / description
eGFR	Estimated glomerular filtration rate
EMA	European Medicines Agency
EoT	End-Of-Text
EOT	End of treatment
EQ-5D	EuroQoL 5 dimensions
EudraCT	European Clinical Trials Database
FG	Fasting glucose
FU	Follow-up
GI	Gastrointestinal
HbA 1c	Glycosylated haemoglobin
HCRU	Health Care Resource Utilisation
HDL-C	High density lipoprotein cholesterol
HF	Chronic Heart Failure
HHF	Hospitalisation for heart failure
HLT	High level term
hsTnT	high-sensitivity troponin T
HR	Hazard ratio
ICD	Implantable Cardioverter Defibrillator
ICH	International Conference on Harmonisation
IPD	Important protocol deviation
IRT	Interactive Response Technology
ITT	Intention-to-treat
IVRS	Interactive voice response system
JFM	Joint frailty model
KCCQ	Kansas City Cardiomyopathy Questionnaire
LVAD	Left ventricular assist device
LDL-C	Low density lipoprotein cholesterol
LLT	Low level term
LVEF	Left ventricular ejection fraction
LVOT	Last value on treatment
LTFU	Lost to follow-up
Max	Maximum

Term	Definition / description
MedDRA	Medical Dictionary for Regulatory Activities
MI	Myocardial infarction
Min	Minimum
MMRM	Mixed models repeated measures
MRA	Mineralocorticoid Receptor Antagonist
Non-CV	Non-cardiovascular
NT pro-BNP	N-terminal pro B-type natriuretic peptide
NYHA	New York Heart Association Classification
OC-AD	Observed Case including data after discontinuation
OC-OT	Observed Case on-treatment
PK	Pharmacokinetic
PAOD	Peripheral Arterial Occlusive Disease
PT	Preferred term
Q1	Lower quartile
Q3	Upper quartile
PDMAP	Project data management and analysis plan
RS	Randomized set
SAE	Serious adverse event
SAS	Statistical Analysis System
SBP	Systolic blood pressure
SCR	Screened set
SD	Standard deviation
SE	Standard error
SGLT-1	Sodium-glucose co-transporter 1
SGLT-2	Sodium-glucose co-transporter 2
SI	Système international d'unités
SMQ	Standardized MedDRA query
SOC	System organ class
TBILI	Total bilirubin
TS	Treated set
TS-FU	Treated set – Follow-up
TSAP	Trial statistical analysis plan

---

Term	Definition / description
UACR	Urine Albumin Creatinine Ratio
ULN	Upper limit of normal
UTI	Urinary tract infection
WHO DD	World Health Organization Drug Dictionary

### **3. INTRODUCTION**

As per the International Conference on Harmonisation (ICH) E9 guidance ([1](#)), the purpose of this document is to provide a more technical and detailed elaboration of the principal features of the analysis described in the protocol, and to include detailed procedures for executing the statistical analysis of the primary and secondary variables and other data.

This Trial Statistical Analysis Plan (TSAP) assumes familiarity with the Clinical Trial Protocol (CTP), including Protocol Amendments. In particular, the TSAP is based on the planned analysis specification as written in CTP Section 7 “Statistical Methods and Determination of Sample Size”. Therefore, TSAP readers may consult the CTP for more background information on the study, e.g., on study objectives, study design and population, treatments, definition of measurements and variables, planning of sample size, randomization.

SAS® Version 9.4 or later will be used for all analyses.

#### 4. CHANGES IN THE PLANNED ANALYSIS OF THE STUDY

1. In the random coefficient model used to estimate slope in change from baseline of eGFR (CKD-EPI)cr, an additional fixed effect term of interaction of eGFR (CKD-EPI)cr at baseline (continuous) by time is included.
2. As per protocol the objective of the trial is “to demonstrate superiority of empagliflozin 10 mg versus placebo”.  
The ITT analysis approach was chosen to as closely as possible reflect real-life conditions, disregarding any occurrences of treatment stop or restart of treatment, that may happen in clinical practice as well.  
However, it is also recognized and recommended by the Steering Committee that the study-specific treatment discontinuation in the close-out period does not resemble clinical practice.  
Therefore for patients that complete the treatment period according to protocol after close-out announcement the time at risk for efficacy endpoints ends at the discontinuation of treatment and events occurring thereafter are not considered in the efficacy analyses.  
The primary estimand is now specified in [Section 7.4](#).  
An analysis including all events after randomization will be conducted as sensitivity analysis for the primary endpoint and the key secondary endpoint of recurrent HHF. A corresponding approach will be used for continuous endpoints.
3. Mixed model for repeated measures (MMRM) for KCCQ at week 52 as well as other MMRMs were specified in condensed form to be in line with BI internal standards. Therefore, individual model terms were removed from the MMRM if already included as interaction term with treatment or visit. Additionally, the terms included in MMRMs were aligned throughout the TSAP
4. The rules defining ‘win’ and ‘lose’ for the win ratio calculation were clarified and adapted to also consider the time to first HHF event in case of a tie in the number of HHF events. The adaption was made since time to first HHF event is also considered relevant information to avoid ties in case the number of HHF events is identical. This approach is a modification of the rules applied by Rogers 2014 ([8](#)).
5. In all models (e.g., Cox regression, MMRM, et al.) with LVEF included per protocol as a continuous covariate, it has been changed to a categorical variable ( $\leq 30\%$ ,  $>30\%$  to  $\leq 35\%$ ,  $> 35\%$ ). The reason the change was made was because the inclusion criterion has different NTproBNP thresholds depending on presence or absence of atrial fibrillation and LVEF category. This inclusion criterion stipulates that the relationship between LVEF and outcome events is non-monotonic.

## **5. ENDPOINTS**

### **5.1 PRIMARY ENDPOINT**

The primary endpoint is the composite of time to first event of adjudicated CV death or adjudicated HHF.

For further clarification: Adjudicated CV death always includes death adjudicated as death due to undetermined cause. This is applicable throughout all analyses wherever adjudicated CV death is mentioned.

### **5.2 SECONDARY ENDPOINTS**

#### **5.2.1 Key secondary endpoints**

Key secondary endpoints are:

- Occurrence of adjudicated HHF (first and recurrent)
- eGFR (CKD-EPI)cr slope of change from baseline

#### **5.2.2 Other Secondary endpoints**

Other secondary endpoints are specified in the CTP Sections 5.1.2 and 5.2, and in TSAP [Section 7.5.2](#).

### **5.3 FURTHER ENDPOINTS**

Further endpoints are listed in the CTP Section 5.1.3, and in TSAP [Section 7.6](#). The definition and assessment can be found in Section 5.2.

Further endpoints added include:

- Time to non-cardiovascular (non-CV) death (i.e. death cases not included in the definition of adjudicated CV death)
- Fasting glucose (FG) change from baseline to last value on treatment (LVOT) and follow-up (FU), overall and by status of diabetes mellitus (DM)
- Time to first investigator-defined CV hospitalization. Investigator-defined CV hospitalization includes AEs ticked by the investigator as “CV hospitalization (due to reasons other than heart failure, MI or stroke)” and AEs ticked as “Hospitalization for Heart failure” as well as events ticked as “Cardiovascular (CV) Death other than CV death attributed to myocardial infarction or stroke”, MI, stroke, non-fatal TIA that are reported as requiring hospitalization.
- Time to atrial fibrillation (defined as time to first reported ECG indicating atrial fibrillation or to first AE with PT atrial fibrillation).

## **5.4 OTHER VARIABLES**

### **5.4.1 Kansas City Cardiomyopathy Questionnaire (KCCQ) scores**

There are 10 summary scores within the KCCQ, which are calculated as follows:

#### 1. Physical Limitation

Code responses to each of Questions 1a-f as follows:

- Extremely limited = 1
- Quite a bit limited = 2
- Moderately limited = 3
- Slightly limited = 4
- Not at all limited = 5
- Limited for other reasons or did not do = <missing value>

If at least three of Questions 1a-f are not missing, then the Physical Limitation Score is calculated as follows:

Physical Limitation Score =  $100 * [(\text{mean of Questions 1a-f actually answered}) - 1] / 4$

#### 2. Symptom Stability

Code the response to Question 2 as follows:

- Much worse = 1
- Slightly worse = 2
- Not changed = 3
- Slightly better = 4
- Much better = 5
- I've had no symptoms over the last 2 weeks = 3

If Question 2 is not missing, then the Symptom Stability Score is calculated as follows:

Symptom Stability Score =  $100 * [(Question\ 2) - 1] / 4$

#### 3. Symptom Frequency

Code responses to Questions 3, 5, 7 and 9 as follows:

Question 3

- Every morning = 1
- 3 or more times a week but not every day = 2
- 1-2 times a week = 3
- Less than once a week = 4
- Never over the past 2 weeks = 5

Questions 5 and 7

- All of the time = 1
- Several times a day = 2
- At least once a day = 3
- 3 or more times a week but not every day = 4
- 1-2 times a week = 5
- Less than once a week = 6
- Never over the past 2 weeks = 7

Question 9

- Every night = 1
- 3 or more times a week but not every day = 2
- 1-2 times a week = 3
- Less than once a week = 4
- Never over the past 2 weeks = 5

If at least two of Questions 3, 5, 7 and 9 are not missing, then the Symptom Frequency Score is calculated as follows:

$$S3 = [(Question\ 3) - 1]/4$$

$$S5 = [(Question\ 5) - 1]/6$$

$$S7 = [(Question\ 7) - 1]/6$$

$$S9 = [(Question\ 9) - 1]/4$$

Symptom Frequency Score =  $100 * (\text{mean of S3, S5, S7 and S9})$

#### 4. Symptom Burden

Code responses to each of Questions 4, 6 and 8 as follows:

- Extremely bothersome = 1
- Quite a bit bothersome = 2
- Moderately bothersome = 3
- Slightly bothersome = 4
- Not at all bothersome = 5
- I've had no swelling/fatigue/shortness of breath = 5

If at least one of Questions 4, 6 and 8 is not missing, then the Symptom Burden Score is defined as follows:

Symptom Burden Score =  $100 * [(\text{mean of Questions 4, 6 and 8 actually answered}) - 1] / 4$

#### 5. Total Symptom Score

The Total Symptom Score is defined as the mean of the following available summary scores:

Symptom Frequency Score and Symptom Burden Score

#### 6. Self-Efficacy

Code responses to Questions 10 and 11 as follows:

Question 10

- Not at all sure = 1
- Not very sure = 2
- Somewhat sure = 3
- Mostly sure = 4
- Completely sure = 5

Question 11

- Do not understand at all = 1
- Do not understand very well = 2

- Somewhat understand = 3
- Mostly understand = 4
- Completely understand = 5

If at least one of Questions 10 and 11 is not missing, then the Self-Efficacy Score is calculated as:

$$\text{Self-Efficacy Score} = 100 * [(\text{mean of Questions 10 and 11 actually answered}) - 1] / 4$$

#### 7. Quality of Life

Code responses to Questions 12, 13 and 14 as follows:

##### Question 12

- It has extremely limited my enjoyment of life = 1
- It has limited my enjoyment of life quite a bit = 2
- It has moderately limited my enjoyment of life = 3
- It has slightly limited my enjoyment of life = 4
- It has not limited my enjoyment of life at all = 5

##### Question 13

- Not at all satisfied = 1
- Mostly dissatisfied = 2
- Somewhat satisfied = 3
- Mostly satisfied = 4
- Completely satisfied = 5

##### Question 14

- I felt that way all of the time = 1
- I felt that way most of the time = 2
- I occasionally felt that way = 3
- I rarely felt that way = 4
- I never felt that way = 5

If at least one of Questions 12, 13 and 14 is not missing, then the Quality of Life Score is calculated as:

$$\text{Quality of Life Score} = 100 * [(\text{mean of Questions 12, 13 and 14 actually answered}) - 1] / 4$$

#### 8. Social Limitation

Code responses to each of Questions 15a-d as follows:

- Severely limited = 1
- Limited quite a bit = 2
- Moderately limited = 3
- Slightly limited = 4
- Did not limit at all = 5
- Does not apply or did not do for other reasons = <missing value>

If at least two of Questions 15a-d are not missing, then the Social Limitation Score is calculated as:

$$\text{Social Limitation Score} = 100 * [(\text{mean of Questions 15a-d actually answered}) - 1] / 4$$

#### 9. Overall Summary Score

The Overall Summary Score is defined as the mean of the following available summary scores:

Physical Limitation Score, Total Symptom Score, Quality of Life Score and Social Limitation Score

#### 10. Clinical Summary Score

The Clinical Summary Score is defined as the mean of the following available summary scores:

Physical Limitation Score and Total Symptom Score

---

Note: references to “means of questions actually answered” imply the following.

If there are n questions in a scale, and the subject must answer m to score the scale, but the subject answers only n-i, where n-i >= m, calculate the mean of those questions as

(sum of the responses to those n-i questions) / (n-i)

not

(sum of the responses to those n-i questions) / n

Patient-preferred outcome is derived from response to the question about which domain is the most difficult for the patient to cope with at baseline:

- Loss of functional abilities: Physical Limitation Score
- Symptoms due to your heart failure: Total Symptom Score
- Your concern about how to manage your heart failure: Self-Efficacy Score
- Suffering from depression, anxiety, emotional liability because you have heart failure: Quality of Life Score
- Adapting your life to heart failure: Social Limitation Score

#### **5.4.2 LVEF**

Values of LVEF will be considered valid, when appropriate methodology was used. When methodology is missing, LVEF will be disregarded.

## 6. GENERAL ANALYSIS DEFINITIONS

### 6.1 TREATMENTS

There will be 4 basic treatment phases in this trial: screening, study treatment phase (with either empagliflozin 10mg or matching placebo), post-treatment and post-study. However, during the study treatment phase, patients are allowed to go off-treatment and subsequently re-start treatment. This may happen not at all or repeatedly for a given patient.

The purpose of the definitions below is to describe all the different study/treatment intervals, in which a patient can lie during the course of the trial. Note that the term "treatment regimen" also covers the "off-treatment" time periods.

Table 6.1: 1 Treatment regimens / study intervals

Label	Interval	Start date
Screening	Screening	Date of informed consent
Placebo/ Empagliflozin 10mg	Treatment	Date of first administration of double-blind study treatment
Off-treatment (if applicable)	During Treatment interval, but not on treatment	Date of last administration of the study medication before temporarily discontinuation + 1 day
Placebo/ Empagliflozin 10mg (if applicable)	During Treatment interval, after restart of study medication	Date study medication re-started
Post-treatment	Post-treatment	Date of last administration of study drug + 1 day
Post-study	Post-study	Date of trial completion +1 day

Details on the definition of on-treatment period for different endpoints are listed in [Table 6.1:2](#). The efficacy analyses will follow the intention-to-treat (ITT) principle in assigning patients to treatment groups, i.e. patients will be analysed as randomised.

Safety analyses will also assign patients to the treatment group as randomized.

If a patient erroneously receives the wrong trial drug, all subsequent medication packs dispensed to the patient will still be for the treatment group to which the patient was randomized. Therefore the adverse events will be analyzed as per randomized treatment, which is expected to reflect the prevailing treatment.

In the exceptional case that a patient took the wrong treatment, adverse events may occur while being on the wrong treatment. Analyses of this data are described in [Section 7.8.1.6](#).

Table 6.1: 2 Endpoint specific assignment to the on-treatment phase

Endpoint	Last day of assignment to the on-treatment phase (days after last intake of study medication)
Adverse events	7
Safety laboratory measurements, including Urine Albumin Creatinine Ratio (UACR)	3
Heart rate	1
Glycosylated haemoglobin (HbA 1c )	7
FG	1
Body weight	1
Creatinine and estimated glomerular filtration rate (eGFR)	1
N-terminal pro B-type natriuretic peptide (NT pro-BNP)	1
Blood pressure	1
Patient reported outcome	7

## 6.2 IMPORTANT PROTOCOL DEVIATIONS (IPDS)

A protocol deviation (PD) is important, if it affects the rights or safety of the study patients or if it can potentially influence the primary outcome measures for the respective patients in a way that is neither negligible nor in accordance with the study objectives.

The IPDs will be described in the clinical trial report (CTR). A listing of patients with medication code broken will be provided.

Table 6.2: 1 Important protocol deviations

Category / Code	Description	Requirements	Excluded from
A	Entrance criteria not met		
A1	Target indication not met		
	A1.06 No chronic HF or no NYHA class II-IV	Inclusion criterion #3 not met	None
	A1.07 Conditions on ejection fraction (EF) violated	Inclusion criterion #4 not met	None
	A1.08 Conditions on NT-proBNP violated	Inclusion criterion #5 not met	None
A2	Inclusion criteria not met		
	A2.02 Age out of range	Inclusion criterion #1 not met	None
	A2.08 Specific inclusion criterion for women of child-bearing potential violated	Inclusion criterion #2 not met	None

Table 6.2: 1 Important protocol deviations (cont.)

Category / Code	Description	Requirements	Excluded from
A2.13	Use of medical devices not appropriate or device implanted recently or intent to implant	Inclusion criterion #7 not met	
A3	Exclusion criteria met		
A3.44	Patient with unstable conditions	Exclusion criteria #1, #2, #6, #8, #10, #13, or #18 met	None
A3.28	Currently implanted left ventricular assist device (LVAD)	Exclusion criterion #3 met	None
A3.29	Patients with cardiomyopathies as defined in the protocol	Exclusion criterion #4 met	None
A3.30	Any severe (obstructive or regurgitant) valvular heart disease, obstructive or regurgitant, or any valvular disease expected to lead to surgery during the trial in the opinion of the investigator	Exclusion criterion #5 met	None
A3.31	Atrial fibrillation or atrial flutter with a resting heart rate >110bpm	Exclusion criterion #7 met	None
A3.32	Diagnosis of cardiomyopathy induced by chemotherapy or peripartum	Exclusion criterion #9 met	None
A3.33	Systolic blood pressure at visit 1 or 2 out of range	Exclusion criterion #11 or #12 met	None
A3.06	Indication of liver disease	Exclusion criterion #14 met	None
A3.09	Renal insufficiency or renal impairment (assessed by eGFR)	Exclusion criterion #15 met	None
A3.34	Haemoglobin at visit 1 below cut-off	Exclusion criterion #16 met	None
A3.35	History of Ketoacidosis	Exclusion criterion #17 met	None
A3.36	Gastrointestinal (GI) surgery or GI disorder that could interfere with study medication absorption in the investigator's opinion	Exclusion criterion #19 met	None
A3.37	Documented or active malignancy	Exclusion criterion #20 met	None
A3.38	Life expectancy of <1 years in the opinion of the investigator	Exclusion criterion 21 met	None
A3.39	Intake of restricted medications or any drug considered likely to interfere with the safe conduct of the trial	Exclusion criterion #22 met	None
A3.40	Treatment with any SGLT-2 inhibitor or SGLT-1 and 2 inhibitor	Exclusion criterion #23 met	None
A3.11	Intake of an investigational drug in another trial within 30 days prior to intake of study medication in this trial	Exclusion criterion #24 met	None
A3.41	Known allergy or hypersensitivity to empagliflozin	Exclusion criterion #25 met	None
A3.13	Relevant alcohol or drug abuse and condition affected study compliance	Exclusion criterion #26 met	None
A3.12	Specific exclusion criterion for premenopausal women violated	Exclusion criterion #27 met	None
A3.14	Any other clinical condition unsafe for participation	Exclusion criterion #28 met	None
A3.53	Recently implanted ICD/CRT or intent to implant	Exclusion criterion #29 met	None

Table 6.2: 1 Important protocol deviations (cont.)

Category / Code	Description	Requirements	Excluded from
B	Informed consent		
B1	Informed consent not available/not done	Informed consent date missing or inclusion criterion #9 met	All
B2	Informed consent too late	Informed consent date was after Visit 1	None
C	Trial medication and randomisation		
C1.02	Incorrect trial medication taken	Wrong medication taken for more than 20% of the overall treatment duration Can only be finally judged after data base lock (DBL) since unblinding information is required.	None
D	Concomitant medication		
D2.02	Use of prohibited medication	Use of SGLT-2 or combined SGLT-1 and 2 inhibitors after randomization but before the EOT visit occurring at study close out	None

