6. Appropriate dose of medical therapy for HF (such as ACEi, ARB, β -blocker, oral diuretics, MRA, ARNI, ivabradine) consistent with prevailing local and international CV guidelines, stable for at least 1 week prior to Visit 1 and during screening period until Visit 2 (Randomisation) with the exception of diuretics stable for only one week prior to Visit 2 to control symptoms. The investigator must document in the source documents the reason why patient not on target dose per local guidelines
7. Appropriate use of medical devices such as cardioverter defibrillator (ICD) or a cardiac resynchronization therapy (CRT) consistent with prevailing local or international CV guidelines (refer also to exclusion #29)
8. Body Mass Index (BMI) $<$ 45 kg/m² at Visit 1 (Screening)
9. Signed and dated written ICF in accordance with Good Clinical Practice (GCP) and local legislation prior to admission to the trial

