10.1.2 Patient information and informed consent (including biobanking)

In the event of recruiting an illiterate patient, the following process should be followed with respect to patient information and ICF:

- The designated site personnel performing the ICF process will read the trial approved patient information sheet and ICFs to the patient, and explain the details of the trial, all in the presence of an impartial witness.
- This impartial witness must be literate, and can be the patient's relative or caregiver, or a member of staff employed by the clinic but not part of the immediate trial team. In addition, if there are any further local regulations with respect to the consent of illiterate patients, these should also be followed.
- The requirements of the trial will be explained thoroughly and the patient will be given ample time to ask questions and consider his/her participation. If he/she wishes, the patient can take the patient information sheet and ICFs home for further consideration.
- If patient agrees to take part in the trial, he/she would then return to the clinic for the consent process to be completed. The site designated personnel responsible for this process will confirm that the patient has no further questions in the presence of the same

Proprietary confidential information © 2019 Boehringer Ingelheim International GmbH or one or more of its affiliated companies

impartial witness (if the patient returns on another day). If a different impartial witness is present, the entire ICF process must be repeated.

- Participating patients will provide a thumb impression or make a mark (or signature if the patient is able to sign him/herself) on the signature section of the ICF forms.
- The date of the patient's signature will be left blank as the patient is illiterate. However, if the patient is able, he/she will date the mark/signature personally.
- The impartial witness or the site designated personnel may write the name of the patient on the ICFs.
- The impartial witness should enter his/her name, sign and personally date the witness section of the ICFs. In countries where local data protection regulation permits it, the address or identification number of the impartial witness should also be entered. The signature then attests that the content of the patient information sheet ICF was accurately explained to the patient, who apparently understood and freely gave consent to participate in the trial.

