### 6.3 SUBJECT SETS ANALYSED

The following patient sets are defined

- *Screened Set (SCR)*  
Consists of all patients screened for the trial, with informed consent given and who completed at least one screening procedure at Visit 1.
- *Randomised set (RS)*  
This patient set includes all randomised patients, whether treated or not.
- *Treated set (TS)*  
This patient set includes all patients who were dispensed study medication and were documented to have taken at least one dose of investigational treatment.
- *Treated Set-Follow-up (TS-FU)*  
All patients in the TS, for whom a follow-up visit was performed (i.e. values of planned assessments- KCCQ, EQ-5D, vital signs or lab data reported) between 23 and 45 days after last intake of study medication.

The TS-FU does not include patients, where no planned measurements were taken, which may happen in case of telephone FU visits. Patients with intake of open label SGLT-2 inhibitor between their EOT and FU visit are also excluded from the TS-FU set.

- *Pharmacokinetic Set (PKS)*  
This patient set includes all evaluable patients of the treated set who provide at least one observation for at least one further PK endpoint of Cpre,ss,N for empagliflozin.

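### SAP Table 6.2:1, code B1: the consent deviation that excludes patients from all analyses is triggered by the consent criterion being met, when it should be not met

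*SAP*

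**What the plan says.** SAP section 6.2, Table 6.2:1, gives each important protocol deviation a description, a requirement that triggers it, and an entry under "Excluded from".

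- **B1.** The description is "Informed consent not available/not done", the requirement is "Informed consent date missing or inclusion criterion #9 met", and the exclusion entry is All.
- **B2.** The next row covers consent dated after Visit 1. Its exclusion entry is None.
- **Other inclusion-criterion rows.** These cover #1, #2, #3, #4, #5 and #7, and all use the same form, for example "Inclusion criterion #3 not met".

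Protocol section 3.3.2 defines inclusion criterion #9 as "Signed and dated written ICF in accordance with Good Clinical Practice (GCP) and local legislation prior to admission to the trial".

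For the randomised set (RS), SAP section 6.3 states: "This patient set includes all randomised patients, whether treated or not". Protocol section 7.3 and SAP section 7.4.1 base the primary analysis on this set.

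For illiterate patients, Protocol Appendix 10.1.2 says: "The date of the patient's signature will be left blank as the patient is illiterate". It then adds that "if the patient is able, he/she will date the mark/signature personally". The same appendix has the impartial witness and the designated site personnel each date the form.

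**The concern.** Meeting an inclusion criterion is a condition of entry, so it cannot define a deviation. B1's trigger therefore contradicts its own description, the criterion it cites and the parallel rows in the same table.

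The position of the error is what makes it worth raising. Every other completed cell in the exclusion column says None, and the cell for A2.13 is blank. B1 is thus the only deviation in the table that takes randomised patients out of the analyses, including the primary one. A rule that removes patients after randomisation should be unambiguous before unblinding. According to the SAP history table, section 6.2 was edited in both the October and November 2019 revisions, and the wording is still in the current text.

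**Working it through.** No design figure is involved, so the check is logical.

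**Step 1: truth table.** The inputs are the two conditions in B1 (is the consent date missing, and is criterion #9 met) and its consequence, exclusion from all analyses. The rule as written is compared with the same rule after changing *met* to *not met*.

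| Consent date | Criterion #9 | As written | With *not met* |
|---|---|---|---|
| Present | Met | Excluded | Kept |
| Present | Not met | Kept | Excluded |
| Missing | Met | Excluded | Excluded |
| Missing | Not met | Excluded | Excluded |

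The first two rows are reversed. As written, the only patients kept are those with a recorded date whose consent fails #9. The missing-date part of the trigger points the right way; only the part that cites #9 is inverted.

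**Step 2: does inserting one word suffice?** Criterion #9 includes a timing condition, because consent must precede admission to the trial. A patient whose consent is dated after Visit 1 could therefore fail #9 and, under a bare correction to *not met*, fall under B1 and be excluded from everything. B2 covers late consent and excludes such patients from nothing. The bare correction would make the two rows conflict, so the timing element has to be carved out of B1.

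**Step 3: B1 against the analysis sets.** B1 says All. The RS definition takes in every randomised patient, and the treated set (TS) requires only that study medication was dispensed and at least one dose documented as taken. Neither carries a consent condition. Section 6.3 does write such conditions into a set where they are wanted: the screened set requires that consent was given, and the follow-up treated set excludes patients who took an open-label SGLT-2 inhibitor between the end-of-treatment and follow-up visits. A programmer cannot satisfy both 6.2 and 6.3 for a randomised B1 patient.

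**Step 4: which date is the consent date?** B1 does not say whose date it means. SAP Table 6.1:1 starts the screening interval at the date of informed consent, and B2 uses that date as well, but neither defines it. SAP section 6.6.2 has rules for several kinds of missing date and none for consent. Under Appendix 10.1.2 only the patient's own date may be blank, while the witness and site-personnel dates are on the form. After correction, a patient consented this way is in the first row of the table (kept) if one of those dates is recorded. The patient moves to a missing-date row only if the patient's own blank date is the one captured.

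**The case against.** The strongest answer is that this is a self-evident slip. The row's description states the intent, and the row follows a long run of exclusion-criterion rows that correctly end in *met*, which may be how the word got there. Literal application would leave essentially no validly consented patient in any analysis, so it could not pass unnoticed. This stands: a reader might infer that the primary analysis is at real risk of losing nearly all its patients, and the documents do not support that. It does not follow that the cell can be left as it is, because the table is the operative specification.

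A second answer is that the exclusion column overlays the set definitions, and that the screened set already presupposes consent. That partly stands as an account of what was meant. The RS and TS definitions still carry no such exception, so the two sections need to be reconciled.

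A reader might also infer that illiterate patients consented exactly as Appendix 10.1.2 directs would be dropped because their date is blank, and might attach patient and event counts to that. The documents do not show this. B1 does not refer to a patient-entered date, two other people date the form, and a form dated under the protocol's own procedure can fairly be called dated. The documents give no rate of illiteracy or of missing consent dates. Any count would need an assumed rate and would also presume that the witness and site dates are ignored.

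**Conclusion.** The point holds as an internal error in an operative rule. The B1 requirement is inverted with respect to criterion #9, in the only deviation that excludes patients from all analyses. Two consequences need attention in the same edit: the overlap with B2 that a one-word correction would create, and the mismatch between B1's All and the RS and TS definitions.

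Read literally, the rule reaches every validly consented patient, in principle nearly all of the roughly 3600 planned in SAP section 9.6. That is a statement about the wording, not an expected outcome, since the intent is clear from the description. The number of patients who genuinely lack valid consent is not given and cannot be estimated from the documents. No sample size, power or alpha figure changes. The question of the illiterate patient's date is a minor clarification, conditional on how the consent date is captured.

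**What to change.** 1. In Table 6.2:1, change the B1 requirement to: *no valid informed consent obtained (inclusion criterion #9 not met for reasons other than timing)*. Late consent stays with B2 and its entry of None.
2. State in section 6.3 whether B1 patients leave the RS and TS. If they do, add the exception to those definitions; if they do not, change the B1 exclusion entry to match.
3. As a minor clarification, state that when the patient's own date is left blank under Appendix 10.1.2, the date entered by the witness or the site personnel is the consent date.

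The cost is one table cell and a few sentences in the SAP, made before unblinding. The exclusion entry for B1 changes only if the second option in item 2 is chosen. No new data and no change to the design are needed.
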